9.3.1. Derived Data

AE onset day is calculated as (date of AE start - date of double-blind first dose + 1). The onset day will be missing if the start date is missing or partially missing.

9.3.2. Data Summarization

AE summary tables are listed below:

- An overall summary of the number and percentage of subjects reporting any TEAEs, serious TEAEs, treatment-related TEAEs, serious TEAEs, serious treatment-related TEAE, any TEAEs leading to treatment discontinuation, any TEAEs leading to subject discontinuation and TEAEs leading to death.
- TEAEs overall and by SOC and PT
- TEAEs by severity, overall and by SOC and PT
- Serious TEAEs, overall and by system organ class and preferred term

- TEAEs by relationship to study treatment, overall and by system organ class and preferred term
- TEAEs leading to treatment discontinuation, overall and by SOC and PT
- TEAEs leading to study discontinuation, overall and by SOC and PT
- Most common TEAEs. Most common TEAEs are defined as TEAEs that occur in > 5% of the subjects in either of the treatment groups.
- Serious treatment-related TEAEs, overall and by SOC and PT.

For summary tables, subjects having more than 1 event with the same PT will be counted once for that term. Subjects having more than 1 event with the same SOC will be counted once for each event and once for that SOC. For tabulations by severity, only a subject's most severe event within the category (e.g. overall, SOC, PT) will be counted; similarly, for tabulations by relationship, only a subject's most related event within a category will be counted. The denominator for percentages will be the number of subjects in the Safety Analysis Set for the given treatment group (i.e., the N's for the columns).

Listings will be provided for all AEs and the following subsets:

- All TEAEs at least possibly related to study treatment
- Serious AEs
- AEs leading to treatment discontinuation
- AEs leading to death.

Additional information will be collected for diabetic ketoacidosis (DKA). These data will be listed.

9.3.3. AE of Special Interest

AE of special interest include UTI, pyelonephritis urosepsis, GMI, diuretic effects including hypovolemia, hypotension episodes, hypoglycemia, hepatotoxicity, MACE, fractures, malignancies, hypersensitivity reactions, acid-base disorders including diabetic ketoacidosis, rash, and renal failure events. These AEs of special interest, except for cardiovascular events and amputations, will be prospectively identified based on the MedDRA PTs in the AEs log by a medical expert prior to the data base lock and unblinding of the individual subject treatment assignment. The list of AEs of special interest will be confirmed in a peer review process. Cardiovascular events, hypoglycemia events by severity, and amputations will be summarized separately.

9.3.3.1. AE of special interest identified by PTs

Cardiovascular events considered as MACE by investigator will be submitted to an independent Cardiovascular Endpoint Committee (CEC) for adjudication. The events of interest include all-cause mortality, cardiovascular mortality, MI, stroke, hospitalization for acute coronary syndromes, urgent revascularization procedures, and other possible serious cardiovascular events. Other AE of special interest will be identified from the PTs. The number and percentage of subjects experiencing these TEAEs of special interest will be summarized for each treatment group by type of event. The incidence rate of AE of special interest per 100 patient years will also be summarized. Each category of events will be displayed in a listing.

9.3.3.2. Hypoglycemic Events

Hypoglycemic event categories include:

Category	Description
Severe	Assistance required and blood glucose ≤ 70 mg/dL or no value available but responded to glucose treatment
Documented Symptomatic	Blood glucose ≤ 70 mg/dL and typical symptoms of hypoglycemia
Asymptomatic	Blood glucose ≤ 70 mg/dL and no typical symptoms of hypoglycemia
Probable Symptomatic	Typical symptoms of hypoglycemia and no value available but responded to glucose treatment
Relative	Typical symptoms of hypoglycemia and blood glucose > 70 mg/dL

While each event meeting the criteria above will be entered into the hypoglycemia log, only critical (severe) hypoglycemia, documented symptomatic hypoglycemia, asymptomatic hypoglycemia, and probable hypoglycemia will be entered as AEs.

The number and percentage will be summarized by treatment for:

- Each category of hypoglycemic events;
- Any severe or documented hypoglycemic events.

9.3.3.3. Revascularization and Amputations

Revascularization and amputations information are collected in a separate form. Frequency and percentage will be summarized for:

- Type of cardiovascular related procedures -or amputation
- Subjects with any amputation
- Conditions that resulted in amputation

- Location of amputation

Only procedures performed after the first dose of double-blind study drug will be summarized.

9.4. LABORATORY EVALUATIONS

Laboratory tests will include hematology panel, chemistry panel, serum lipids, and urinalysis testing. Hematology and chemistry will be performed at the following time points: at the screening visit (Week - 11), on baseline visit (Day -3 to -5), and at weeks 6, 24, 48, 60, 96, and 98. Urinalysis will be performed at the following time points: at the screening visit (Week - 11), on baseline visit (Day -3 to -5), and at weeks 6, 12, 24, 36, 48, 60, 72, 96 and 98. Serum lipids will be performed at the screening visit (Week - 11), on baseline visit (Day -3 to -5), and on weeks 24, 60, 96, and 98. Renal functional testing by UACR will be determined at the screening visit, on baseline visit and at Week 60. The study staff will contact each subject prior to a scheduled clinic visit to confirm the time of the visit and to remind the subject of proper fasting practice. A subject must be queried to assess compliance with an approximately 10-hour fast prior to blood draw to ensure the FPG and triglycerides values can be accurately determined. If a subject has not fasted for approximately 10 hours, the subject must return as soon as can be arranged (within 1 week) to provide a specimen after proper fasting. A list of laboratory tests is included in Table 4.

Low density lipoprotein cholesterol (LDL-C) will be calculated by the Friedewald equation. If triglycerides are > 400 mg/dL, the calculated LDL-C value is invalid by this equation and will be set as missing. The following algorithm will be used to obtain LDL-C values for the analyses:

1. Select subjects (based on the SI unit) who had screening triglycerides >3.4 or >350 based on the conventional unit
2. Take the LDL - direct measurement values only, throughout the study visits for those subjects
3. If screening triglycerides > 350 and no direct LDL-C values have been determined, take the calculated.

Among those subjects who have screening triglycerides >350 and have both calculated and direct LDL values, only take the direct LDL.

Urinalysis microscopy will be conducted if the subject has a positive result on the leukocyte esterase or nitrite dipstick tests to clarify the significance of the finding. Results of glucose measurement in the urinalysis must be suppressed from the laboratory reports so the sponsor, investigators, study coordinators, pharmacists, study subjects, and the CEC members will remain blinded to the dosing assignment.

The baseline value will be the latest value obtained prior to Day 1. Change from

baseline for all continuous parameters will be calculated as the post-baseline value minus the baseline value.

Data summaries will use descriptive statistics (number of subjects [n], mean, standard deviation [SD], median, minimum and maximum) for continuous variables, and frequency and percentage of subjects for categorical and ordinal variables

Observed values (in SI units) and change from baseline over time will be summarized by treatment group. Laboratory data will be classified as low, normal, or high relative to the parameter's reference range. Laboratory abnormalities for each treatment will also be summarized with shift tables for selected parameters.

Table 4 List of Laboratory Tests

Test Name (sample volume)		
Hematology (2 mL blood)		

 • Mean corpuscular hemoglobin (MCH) • Mean corpuscular hemoglobin concentration (MCHC) 	
 • Mean corpuscular volume (MCV) • White blood cell (WBC) count with differential 	
 • Red blood cell (RBC) count • Hematocrit (Hct) • Hemoglobin (Hgb) • Platelet count
Serum Chemistry and Electrolytes (3 mL serum)		

 • Albumin (ALB) • ALT • AST • Blood urea nitrogen (BUN) • Creatinine • Uric acid 	
 • Calcium (Ca) • Magnesium • Phosphorus • Potassium (K) • Sodium (Na) • Total Protein 	
 • Glucose • Bicarbonate (HCO₃) • Chloride (Cl) • Total bilirubin • Direct bilirubin
Glycemic Control (2 mL plasma, 2 mL blood)		

 • FPG 	
 • HbA_{1c} 	
Serum Lipids		

 • Total cholesterol (TC) • High-density lipoprotein cholesterol (HDL-C) 	
 • Low-density lipoprotein cholesterol (LDL-C), calculated, or • LDL-C, direct 	
 • Triglycerides (TG)
Infectious Disease Testing (3 mL serum)		

 • Hepatitis B surface antigen (HBsAg) 	
 • Hepatitis C virus (HCV) 	
Urinalysis		

 • Appearance • Bilirubin • Color • Glucose (blinded) • Ketones 	
 • Microscopic examination of sediment • Nitrite • Leukocyte esterase • Occult blood 	
 • pH • Protein • Specific gravity • Urobilinogen
Renal Functional Test		

 • UACR 		
Urine Pregnancy Test		

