6.9.2 Sample Collection, Storage, and Shipping

6.9.2.1 Hematology, Blood Chemistry, Serum Lipids, and Glycemic Control Assessments

Blood samples for hematology, chemistry, serum lipids and glycemic control assessments will be collected. Subjects will be in a seated or supine position during blood collection. Samples will be collected at the time points indicated in the schedule of events in [Appendix 1](#) and [Appendix 2](#).

The study staff will contact each subject prior to a scheduled clinic visit to confirm the time of the visit and to remind the subject of proper fasting practice. A subject must be queried to assess compliance with an approximately 10 h fast prior to blood draw to ensure the FPG and triglycerides values can be accurately determined. If a subject has not fasted for approximately 10 h, the subject must return as soon as can be arranged (within 1 week) to provide a specimen after proper fasting.

Low-density lipoprotein-cholesterol (LDL-C) will be calculated by the Friedewald equation. If triglycerides are > 400 mg/dL, the calculated LDL-C value is invalid by this equation and will be set as missing. Direct LDL-C will be determined in subjects whose triglycerides are > 350 mg/dL at screening visit. All subsequent LDL-C of these subjects will be determined by the same direct LDL-C measurements only.

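### SAP 9.4 pairs a triglyceride cut-off of 3.4 in SI units with 350 in conventional units; 350 mg/dL is about 3.95 mmol/L, and applying the SI figure could leave some subjects with no LDL-C value

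*SAP*

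**What the plan says.** SAP 9.4 (Laboratory Evaluations) sets out how the LDL-C value for analysis is chosen.

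- **General rule.** LDL-C is calculated by the Friedewald equation, with one limit: "If triglycerides are > 400 mg/dL, the calculated LDL-C value is invalid by this equation and will be set as missing".
- **Step 1.** Working from the SI unit, it picks out subjects "who had screening triglycerides >3.4 or >350 based on the conventional unit". Neither number carries a printed unit.
- **Step 2.** "Take the LDL - direct measurement values only, throughout the study visits for those subjects".
- **Step 3.** "If screening triglycerides > 350 and no direct LDL-C values have been determined, take the calculated". A closing sentence adds that subjects above 350 at screening who have both kinds of value contribute only the direct one.

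Protocol 6.9.2.1 decides who has a direct measurement at all: "Direct LDL-C will be determined in subjects whose triglycerides are > 350 mg/dL at screening visit". It then uses the direct method for those subjects at all later visits.

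On reporting, SAP 9.4 says: "Observed values (in SI units) and change from baseline over time will be summarized by treatment group".

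**The concern.** Step 1 reads as a single threshold written twice, once for each unit system. If the two numbers disagree, the choice of limb decides who is selected, and selection decides which LDL-C values may be used.

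The SI number is the lower one. Applying it pulls in subjects below the protocol's threshold for direct measurement. Step 2 then admits only direct values for subjects who are not scheduled to have any. What is at stake is the loss of usable calculated LDL-C in a group defined by its triglyceride level, in the descriptive lipid data.

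**Working it through.** **Inputs**

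- SI cut-off 3.4 and conventional cut-off 350: SAP 9.4, step 1. I take the units to be mmol/L and mg/dL.
- Direct LDL-C planned only above 350 mg/dL at screening: Protocol 6.9.2.1.
- Fallback to calculated LDL-C only above 350 at screening: SAP 9.4, step 3.
- Calculated LDL-C invalid above 400 mg/dL: SAP 9.4 and Protocol 6.9.2.1.
- Conversion factor k, in mg/dL per mmol/L of triglycerides: not in the documents. Assumed 88.57, with a range of 87.5 to 89.0.

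**Trying to reproduce 3.4**

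mmol/L = (mg/dL) / k.

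- 350 / 88.57 = 3.95. Over the range: 350 / 89.0 = 3.93 and 350 / 87.5 = 4.00. The plan's 3.4 is not reproduced.
- In reverse, 3.4 × 88.57 = 301 mg/dL. Over the range: 3.4 × 87.5 = 297.5 and 3.4 × 89.0 = 302.6.
- Size of the discrepancy: (3.95 − 3.4) / 3.95 = 14%.
- Factor needed to make the pair agree: 350 / 3.4 = 102.9. If 3.4 were a rounded figure (3.35 to 3.45), the needed factor would be 350 / 3.45 = 101.4 to 350 / 3.35 = 104.5. Rounding does not explain the gap.
- A factor borrowed from another analyte does not explain it either: the cholesterol factor gives 350 / 38.67 = 9.05, and the glucose factor gives 350 / 18.016 = 19.4.
- 300 / 88.57 = 3.39, so 3.4 is what 300 mg/dL rounds to. The documents do not say where 3.4 came from.

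**Tracing the algorithm** (k = 88.57, step 1 taken literally as either limb)

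| Screening triglycerides, mg/dL | mmol/L | Selected in step 1 | Direct LDL-C planned by protocol | Step 3 fallback available | LDL-C source |
|---|---|---|---|---|---|
| 290 | 3.274 | no | no | no | calculated |
| 301 | 3.398 | no | no | no | calculated |
| 302 | 3.410 | yes | no | no | none |
| 320 | 3.613 | yes | no | no | none |
| 350 | 3.952 | yes | no | no | none |
| 351 | 3.963 | yes | yes | yes | direct |
| 420 | 4.742 | yes | yes | yes | direct |

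The band with no source runs from about 302 to 350 mg/dL. Using the SI limb alone gives the same result, because it is the wider of the two. Using the conventional limb alone closes the band. So does an SI cut-off of 3.95, apart from rounding at 350 itself (3.952).

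Every subject in the band is below 400 mg/dL at screening, so the SAP's own validity limit does not rule out the calculated value there. At later visits it stays usable wherever that visit's triglycerides do not exceed 400. SAP 9.4 schedules six lipid samples: screening, baseline and weeks 24, 60, 96 and 98.

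**The case against.** The best defence is that the intended rule can be recovered. Step 1 gives 350 as its conventional figure, and 350 also appears in step 3, in the closing sentence of the algorithm and in Protocol 6.9.2.1. Only 3.4 is out of line, and a programmer who worked from the conventional unit would lose nothing. The statement that values are summarized in SI units governs reporting and does not by itself settle how subjects are selected. All of this stands, and it makes the data loss conditional. It does not remove the risk, because step 1 itself tells the reader to select on the SI unit.

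Three stronger conclusions are tempting, and the documents do not support them.

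- **A reader might infer that the SAP sets LDL-C to missing in this band.** It does not say so; it sets values missing only above 400 mg/dL. The gap arises from reading steps 2 and 3 together with the protocol's measurement rule, and a direct value obtained outside that rule would fill it.
- **A reader might infer a biased treatment comparison.** Selection rests on a screening value taken before randomization, so no between-arm bias is expected. LDL-C is not among the primary, secondary or other efficacy endpoints in SAP 4.1 to 4.3. SAP 4.4 does not name lipids among the safety laboratory tests, and the SAP's table index has no separately titled lipid table, although SAP 9 counts serum lipids as safety data.
- **A reader might want a count of affected subjects.** Neither document gives a triglyceride distribution, so any count would be a guess.

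It might also seem that step 3 needs its own 400 mg/dL limit. The sentence just before the algorithm already states that limit.

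**Conclusion.** The SI threshold is wrong as written, at the lowest severity. That 3.4 and 350 are not equivalent is certain for practical purposes: it rests on a standard conversion factor that the documents do not print, and it holds across 87.5 to 89.0.

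The consequence is conditional. Subjects at about 302 to 350 mg/dL could be left without LDL-C if the SI limb is programmed, alone or joined to the other limb, and if no direct value was measured outside the protocol's rule. The effect would be confined to descriptive lipid data and would not touch any efficacy conclusion.

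**What to change.** In SAP 9.4, step 1, replace 3.4 with 3.95 mmol/L and print both units, so that the step reads as 3.95 mmol/L, equivalent to 350 mg/dL. That agrees with step 3, with the closing sentence of the algorithm and with Protocol 6.9.2.1. Print the unit beside 350 in the later lines as well.

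The cost is one number and a few unit labels in the SAP. No new data, protocol amendment or change in study conduct is needed. If the selection has already been programmed, check which cut-off the code uses.

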4.3 Exclusion Criteria

Subjects who exhibit any of the following characteristics will be excluded from the study:

1. Diagnosis of type 1 diabetes mellitus or maturity-onset diabetes of the young (MODY)
2. Current use of injected therapy for treatment of diabetes (insulin or glucagon-like peptide-1 (GLP-1) receptor agonist therapy) or a thiazolidinedione (TZD)
3. Hemoglobinopathy that affects HbA1c measurement
4. Any contraindication to the safe use of sulfonylurea therapy, glimepiride or metformin, including known hypersensitivity reaction
5. Genitourinary tract infection within 6 weeks of screening or history of ≥ 3 genitourinary infections requiring treatment within 6 months from screening
6. Cancer, active or in remission, for < 3 years (non-melanoma skin cancer or basal cell carcinoma or carcinoma *in situ* of the cervix will not be grounds for exclusion)
7. History of alcohol or illicit drug abuse in the past 2 years
8. Evidence of abnormal liver function tests (total bilirubin or alkaline phosphatase > 1.5 x upper limit of normal (ULN) with the exception of isolated Gilbert's syndrome); or alanine aminotransferase (ALT) or aspartate aminotransferase (AST) > 2.5 x ULN
9. Estimated glomerular filtration rate (eGFR), as calculated by the modification of diet in renal disease study equation (MDRD), < 60 mL/min/1.73 m² at screening.
10. Uncontrolled hypertension (systolic blood pressure > 160 mmHg or diastolic blood pressure > 95 mmHg) at Visit V1
11. History of human immunodeficiency virus (HIV) infection
12. Life expectancy < 2 years
13. History of myocardial infarction (MI), unstable angina, stroke, or hospitalization for heart failure within 3 months of screening
14. History of treatment with an investigational drug within 30 days or within 7 half-lives of the investigational drug, whichever is longer
15. Previous treatment with bexagliflozin or EGT0001474 study drug (run-in or double-blind investigational product)
16. Currently or within 3 months of taking any SGLT2
17. Currently participating in another interventional trial
18. Prior renal transplantation or evidence of nephrotic syndrome (defined as a urine albumin-to-creatinine ratio (UACR) > 1500 mg/g at screening).

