6.14.2 Eliciting and Reporting AEs

The investigator will periodically assess each subject for the occurrence of AEs after the subject consents to participation in the study. To avoid bias in collecting information about AEs, the investigator should ask subjects the following question: "How have you felt since you were last checked?" All AEs (serious and non-serious) reported by the subject must be recorded on the source documents and CRFs provided by the sponsor.

It is the investigators responsibility to review the results of all laboratory tests as they become available. For each abnormal laboratory test result the investigator needs to ascertain if the result is a clinically significant change from baseline for that individual subject. This determination, however, does not necessarily need to be made the first time an abnormal value is observed. The investigator may repeat the laboratory test or request additional tests to verify the results of the original laboratory tests. If the laboratory value is determined to be a clinically significant and an abnormal change from baseline for that subject, the result is considered a laboratory AE.

Hypoglycemia is defined as any FPG or SMBG value ≤ 70 mg/dL and documented as described in [Section 6.14.11](#).

Any increase in liver function tests (AST, ALT, or bilirubin) greater than 3 times the ULN for the laboratory utilized will automatically be considered a laboratory AE unless the investigator specifically designates otherwise. In addition, investigators are reminded that any increase in liver function test values that fall below this threshold may be considered clinically significant and entered as an AE if the change is determined to be clinically significant.

In addition, the sponsor's Medical Monitor or its designated personnel must be notified immediately by telephone, email, or fax of any immediately reportable AEs (IRAE) according to the procedure outlined below. Special attention should be paid to recording hospitalization and concomitant medications.

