6.14.10 Hepatotoxicity

If plasma AST and/or ALT concentrations $> 3 \times$ ULN are detected, the investigator will record in the source documents the date corresponding to the date of the laboratory abnormality, the type, frequency, and dose of any concurrent medications or supplements taken by the subject within the 14 days of the detected abnormality; and any symptoms or change in physical exam that have occurred since the prior assessment. The investigator should perform additional laboratory and imaging tests to attempt to establish the cause of the AST and ALT elevations, including ruling out any potential contribution from bone or muscle etiologies.

Any clinically significant increase in hepatic enzymes and specifically any ALT or AST $> 3 \times$ ULN requires immediate repeat test within 48 to 72 h to confirm the hepatic enzyme elevation and should be repeated based on the clinical situation at least every 96 h (4 days) until ALT and AST return to $< 2.5 \times$ ULN. Study medication should be stopped and the event should be reported as a laboratory AE within the CRF if the enzyme elevation is confirmed or worsening.

Hepatotoxicity will be diagnosed and entered as an AE should any of the following occur:

- ALT or AST $> 8 \times$ ULN
- ALT or AST $> 3 \times$ ULN and total bilirubin $> 2 \times$ ULN or INR > 1.5
- ALT or AST $> 3 \times$ ULN with the appearance of fatigue, nausea, vomiting, right upper quadrant pain or tenderness, fever, rash, and/or eosinophilia ($> 5\%$).

In the event of hepatotoxicity, investigational product should be discontinued. If no alternative cause of hepatotoxicity to the study drug is identified, the study drug should not be restarted. If an alternative cause of hepatotoxicity is identified, study drug administration may be resumed after the liver function testing returns to baseline and any related symptoms have resolved. If the liver function abnormalities or related symptoms recur after dosing is resumed, the study drug dosing should be permanently discontinued. The investigator is encouraged to consult with the Medical Monitor regarding diagnostic evaluation for the hepatic enzyme elevations. Consultation with a hepatologist may also be appropriate in some circumstances.

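### No planned table counts subjects who meet the protocol's ULN-based hepatotoxicity criteria: SAP 9.4 grades liver tests only as low, normal or high, and SAP 9.3.3 finds hepatotoxicity by preferred term

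*SAP*

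**What the plan says.** **Protocol.** Section 6.14.10 states "Hepatotoxicity will be diagnosed and entered as an AE should any of the following occur" and gives three criteria:

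- "ALT or AST $> 8 \times$ ULN"
- "ALT or AST $> 3 \times$ ULN and total bilirubin $> 2 \times$ ULN or INR > 1.5"
- ALT or AST above 3 x "ULN with the appearance of fatigue, nausea, vomiting, right upper quadrant pain or tenderness, fever, rash, and/or eosinophilia"

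Section 6.14.2 adds that any rise in AST, ALT or bilirubin "greater than 3 times the ULN for the laboratory utilized will automatically be considered a laboratory AE", unless the investigator decides otherwise. It also lets smaller rises be entered if judged clinically significant. Section 4.3, item 8, excludes subjects with "alanine aminotransferase (ALT) or aspartate aminotransferase (AST) > 2.5 x ULN", so a subject may enter with values above normal up to that limit.

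**SAP.** Section 9.4 plans n, mean, SD, median, minimum and maximum for observed values and changes from baseline. It then says "Laboratory data will be classified as low, normal, or high relative to the parameter's reference range", with shift tables for selected parameters. The index has two chemistry tables: 14.3.4.3 (results and change by visit) and 14.3.4.4 (shift). Section 9.3.3 says that the adverse events of special interest, hepatotoxicity among them, "will be prospectively identified based on the MedDRA PTs in the AEs log by a medical expert" before database lock and unblinding.

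**The concern.** Hepatotoxicity is a named adverse event of special interest, and comparing the incidence of such events between arms is a stated safety objective in both documents. Protocol 3.3.4 leaves the definition of these events to the SAP. For hypoglycemia, SAP 9.3.3.2 carries over the five categories with their glucose threshold. For hepatotoxicity it carries over nothing: ULN stands in the SAP glossary and is not used in its analysis text.

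A reader of the final tables may therefore be unable to say how many subjects in each arm met the protocol's criteria. Large and trivial enzyme rises can fall in the same cell of a shift table or under the same preferred term. A subject with combined transaminase and bilirubin elevation would be visible as such only if the site's entry and its coding made it so.

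**Working it through.** The plan states no figure on this point, so there is none to reproduce. The check applies the SAP's grading and the protocol's criteria to the same values.

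**Rules.** Let x be ALT (or AST) and b total bilirubin, both in multiples of ULN.

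- SAP 9.4: x is high if x > 1, otherwise normal (low values do not matter here).
- Protocol 6.14.10, laboratory part: met if x > 8, or if x > 3 and b > 2. I read the second criterion as transaminase > 3 x ULN with either bilirubin > 2 x ULN or INR > 1.5. INR and symptoms are left out of the illustration.

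**Illustrative values (assumed, not from the documents):**

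| Baseline x | Later x | Later b | SAP shift for ALT | Protocol criterion met |
|---|---|---|---|---|
| 0.8 | 1.05 | 0.5 | normal to high | no |
| 0.8 | 8.5 | 0.5 | normal to high | yes |
| 0.8 | 3.5 | 2.1 | normal to high | yes |
| 1.5 | 1.6 | 0.5 | high to high | no |
| 1.5 | 8.5 | 0.5 | high to high | yes |
| 2.5 | 3.5 | 2.1 | high to high | yes |
| 2.5 | 8.5 | 0.5 | high to high | yes |

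Each shift cell holds both qualifying and non-qualifying subjects. Any subject with a baseline between 1 and 2.5 x ULN who passes 8 x ULN shows no ALT shift. Because each parameter has its own shift, rows three and six cannot be recognized as joint cases.

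**Can the by-visit maximum fill the gap?** Only in part.

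- SAP 6.1 puts a single record per visit into summary tables, and SAP 6.4 picks the one nearest the target day.
- Protocol 6.14.10 requires a repeat within 48 to 72 hours of a value above 3 x ULN and then at least every 4 days, so a peak may well be an unscheduled value.
- The week 24 window runs from Day 126 to Day 209 with target Day 168. A peak on Day 140 is 168 - 140 = 28 days from target and loses to a scheduled sample on Day 168.
- This happens where a scheduled chemistry sample competes. Chemistry is not scheduled at weeks 12, 36 and 72, so in those windows an unscheduled value competes only with other unscheduled ones.
- Shift tables keep all records but discard magnitude; by-visit tables keep magnitude but can discard the peak. Even when the peak is kept, a maximum does not say how many subjects crossed a threshold.

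**Can preferred terms fill the gap?** Also in part. Protocol 6.14.2 and 6.14.10 send qualifying cases to the adverse event log. What reaches the hepatotoxicity row of Table 14.3.1.10 then depends on the site's wording, the coding and the expert's term list. An enzyme-increased term does not record whether the value was above or below 3 x or 8 x ULN.

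**Index.** No title among the tables, figures or listings names a multiple of ULN or a joint transaminase and bilirubin criterion.

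**The case against.** The strongest reply is that the SAP does what the protocol's analysis sections ask. Protocol 9.8.2 plans identification by preferred term, by a medical expert before unblinding and with peer review. Protocol 9.8.3 plans low, normal and high grading with shift tables. Section 6.14.10 is a rule for investigators. This stands: a reader might infer that the SAP departs from the protocol's planned analysis, and it does not. Yet Protocol 9.8.2 also leaves to the SAP further analyses of safety parameters associated with these events, and for liver tests none is given.

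Second, qualifying cases have other routes into the output. They must be entered as adverse events, and section 6.14.10 also ties confirmed or worsening elevations to stopping study medication, so they can appear in the tables of events leading to discontinuation. SAP section 9 promises by-subject listings of all safety data, although the listing index names none for chemistry. This stands too: the cases are not wholly lost, and a complete miss would need a lapse in site entry or in classification.

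Third, a reader might infer that liver tests are reported only as means. They are not; SD, median, minimum and maximum are planned. A reader might also infer that each qualifying subject would change the trial's conclusion. Nothing supports that, because Protocol 9.1 analyzes safety objectives descriptively, with no hepatotoxicity test or limit. With no cases among 210 subjects the one-sided 95% upper bound is 1 - 0.05^(1/210) = 1.4%, but that reflects the sample size and does not measure this gap.

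Finally, the table shells and appendix were not available, so a ULN grading there cannot be ruled out. The index titles give no sign of one.

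**Conclusion.** The point holds as a cheap improvement to the safety reporting. The protocol defines hepatotoxicity by multiples of ULN, and no analysis in the SAP text or its index counts subjects by those criteria. The planned outputs can show that an extreme value occurred and can carry reported cases. They cannot give the number per arm meeting the protocol's criteria, and they cannot show the joint transaminase and bilirubin criterion.

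The effect is confined to one descriptive safety comparison. The missing-shift problem concerns only subjects who enter between 1 and 2.5 x ULN, and the documents give neither their number nor an expected rate of hepatotoxicity, so I put no figure on it. The conclusion assumes that the shells add no ULN grading and that the expert's term list is not supplemented by laboratory values.

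**What to change.** In SAP 9.4 and the table index, add one table by arm for the Safety Analysis Set. It should cover any time after the first double-blind dose and include unscheduled and available local values, each read against its own laboratory's ULN. Give n (%) of subjects with:

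- ALT or AST > 3 x ULN;
- ALT or AST > 8 x ULN;
- ALT or AST > 3 x ULN together with total bilirubin > 2 x ULN, stating how close in time the two values must be, which the protocol does not say.

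Add a listing of these subjects with INR and symptoms where recorded. INR is not in the laboratory panel of Protocol Table 3 or SAP Table 4, so that part of the second criterion will be incomplete.

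In SAP 9.3.3, report subjects meeting the Protocol 6.14.10 criteria alongside the term-based hepatotoxicity result, and reconcile the two. This supplements the preferred-term method and does not replace it.

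The cost is SAP wording, one table and one listing. ALT, AST and total bilirubin are already collected at screening, at baseline and at weeks 6, 24, 48, 60, 96 and 98, plus any repeats. No clinical threshold or stopping rule changes.
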